2.3 Outcome Measures

Primary objective: Usability and feasibility

- Measures:
 - Self-Efficacy for Appropriate Medication Use Scale
 - Beliefs About Medication questionnaire (at baseline)
 - Satisfaction and acceptance questionnaire

Secondary objective: medication adherence

- Measures, Self-reporting:
 - Morisky Medication Adherence Scale
 - Medication Adherence Questionnaire
 - Brief Medication Questionnaire
 - 7-day recall
- Measures, Objective:
 - Electronic data collected by the KARIE device. Adherence may be calculated as the number of dispensed doses/ the total number of prescribed doses during the prescription period *100

3 Procedures

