2.2 Participants

Study participants will include MSK, amputee, neuro rehabilitation and Geriatric Functional Enhancement Service (GFES) inpatients currently receiving care at West Park Healthcare Centre (Toronto) with a home transition plan following discharge. Inclusion criteria will include:

- need to manage medications independently at home;
- stabilized on medication, as per pharmacist/physician discretion; and
- mild-moderate cognitive/physical impairments, as per OT assessment
- Montreal Cognitive Assessment (MoCA) score not less than 16

It is anticipated that 20% of West Park patients will be eligible for SME and will consent to participation in the experimental trial. With 25 patients per unit and an average length of stay of 4-weeks on the MSK, amputee, neuro rehabilitation units, it is anticipated that a recruitment target of 75 experimental and 75 control subjects could be reached within a 10-month time frame (25 pts x 3 units x 20% x 10 months = 150 pts). These 150 patients from West Park will be randomly assigned to the SME (n=75) or SME+K (n=75) group. To meet this target an assumption of 80% compliance will be made. Therefore, up to 94 participants per experimental arm will be recruited. GFES length of stay is comparatively longer at roughly 12 weeks. It is expected that fewer patients will be recruited from GFES, but will contribute toward meeting the recruitment target.

One hundred fifty study participants will be recruited from the CapitalCare CHOICE programs (AB) which assist seniors to continue living independently and in their own home longer by managing all their health requirements. CapitalCare CHOICE clients attend one of three day centres, one to five days a week, and receive services which include ongoing medical, psychological, and social support. The total census for the CapitalCare CHOICE programs is 202 clients and enrollment varies. Initial recruitment will significantly predict how quickly the target of 75 experimental and 75 control subjects can be reached. If after the initial recruitment period suggests challenges meeting the target within the study timeframe, recruitment will be opened up to the CapitalCare Adult Day Program, Laurier House, Post-Acute, Sub-Acute, and Restorative Care clients at CapitalCare's other centres. The focus of these programs is to maintain client independence and autonomy while supporting personal care needs.

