3.4 Data Collection

The study RA will contact each study participant to arrange a data collection session within 24-48 hours prior to discharge. Data collection will include those scales identified in Outcome Measures above. Following discharge to the community, RAs will contact study participants via telephone on a bi-weekly basis to enquire about any missed medications. During these telephone contacts the RA and study participant will review the medication adherence log for the previous 2 weeks.

Data collection will be repeated at 3-months post-discharge. The RA will contact the participant 1-2 weeks prior to completion of the 3-month intervention period to schedule in in-home visit where post-intervention data collection will take place. In addition, the RA will collect participant medication adherence log.

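### Acceptability after home use is scheduled only at 3 months, and carrying the last observation forward cannot supply a valid answer for participants not reached then

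*Combined protocol and SAP*

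**What the plan says.** Section 2.3 (Outcome Measures) opens with "Primary objective: Usability and feasibility" and lists three measures beneath it: a medication self-efficacy scale, a beliefs questionnaire marked as baseline, and the "Satisfaction and acceptance questionnaire". By name, only the third asks about satisfaction or acceptance. The section gives it no timing, respondent group or scoring.

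Section 3.4 (Data Collection) sets two occasions for the scales. The first is before discharge: "The study RA will contact each study participant to arrange a data collection session within 24-48 hours prior to discharge". On what is collected at that session, the section states "Data collection will include those scales identified in Outcome Measures above", which taken literally covers the satisfaction questionnaire. The second is stated as "Data collection will be repeated at 3-months post-discharge", at an "in-home visit where post-intervention data collection will take place". Between the two, "RAs will contact study participants via telephone on a bi-weekly basis to enquire about any missed medications" and to go through the adherence log. No satisfaction item, and no contact triggered by stopping the device or leaving, is described.

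Section 4 (Analysis) handles participants who do not finish the 3 months by intention-to-treat with last-observation-carried-forward (LOCF). Section 2.2 (Participants), in its West Park paragraph, says "To meet this target an assumption of 80% compliance will be made" and raises recruitment from 75 to as many as 94 per arm.

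**The concern.** In a study whose primary objective is usability and feasibility, the views of people who gave up on the device are among the most informative. The plan has no scheduled point at which to hear them if they are not available for the 3-month visit.

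LOCF does not repair this. If the questionnaire is not given before discharge, there is no earlier value. If it is given then, as the wording of section 3.4 implies, the answer follows at most an inpatient orientation to the device (section 3.2.2) and precedes any home use. Carried forward, it would be counted as an experience the participant never reported. The acceptability result would describe those who were reached, or mix their experience with other people's first impressions. Because no reason for stopping or leaving is recorded, the study could not later check whether dissatisfaction drove the losses.

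**Working it through.** **Inputs.** From section 2.2 (West Park): target 75 per arm, 80% compliance, 94 recruited per arm. Reading compliance as completion of the 3 months is an assumption. The documents give no satisfaction rates, so all of those below are assumed.

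**1. The plan's own figure.** 75 / 0.80 = 93.75, rounded up to 94. This reproduces the stated number. No power calculation is given, so there is nothing further to reproduce.

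**2. Possible missing post-use answers in SME+K.** 94 − 75 = 19, and 19 / 94 = 20.2%.

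**3. Completers only.** Let c be the share of completers who find the device acceptable and d the true share among leavers. The share among all 94 is (75c + 19d) / 94, so the overstatement is c − (75c + 19d) / 94 = (19/94)(c − d), or about 0.2 times the gap. A gap of 20 points gives 0.2 × 20 = 4 points, and a gap of 60 gives 0.2 × 60 = 12. With c = 80%:

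| Leavers accepting (d) | Share among all 94 | Overstatement, points |
|---|---|---|
| 20% | (60 + 3.8) / 94 = 67.9% | 12.1 |
| 40% | (60 + 7.6) / 94 = 71.9% | 8.1 |
| 60% | (60 + 11.4) / 94 = 76.0% | 4.0 |
| 80% | (60 + 15.2) / 94 = 80.0% | 0 |
| 90% | (60 + 17.1) / 94 = 82.0% | −2.0 |

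**4. LOCF.** If a share p of the 19 gave a favourable answer before discharge and that is carried forward, the error is 19(p − d) / 94. For d = 20%, 40% and 60%:
- p = 60%: 8.1, 4.0 and 0 points.
- p = 80%: 12.1, 8.1 and 4.0 points.
- p = 90%: 14.1, 10.1 and 6.1 points.

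LOCF is therefore worse than completers-only when p exceeds c, and better when p is below c but still above d. Nothing in the plan fixes which applies.

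**5. Bounds with c = 80%.** If none of the 19 accept, 60 / 94 = 63.8%; if all do, 79 / 94 = 84.0%. The missing answers alone leave a range of 20.2 points.

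**6. Other attrition rates.** For gaps of 20 to 60 points, the completers-only overstatement is 1 to 3 points at 5% attrition (0.05 × 20, 0.05 × 60), 2 to 6 at 10%, and 6 to 18 at 30%.

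**The case against.** Several points on the other side are sound.

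- **Stopping the device is not leaving the study.** A reader might infer that those who give up the device drop out. The documents do not say so. Calls and the home visit are for study participants, not only continuing users, and the analysis is by intention-to-treat. Someone who stops can still answer at 3 months. The gap concerns people not reached then.
- **The 80% is not an abandonment rate.** A reader might infer that a fifth of users would abandon the device. The term is undefined, applies equally to the control arm, which has no device, and appears only in the West Park paragraph. It does not extend to CapitalCare. As 75 is the number left after the allowance, the coherent count is 19 of 94.
- **Overstatement is not certain.** If people leave for reasons unrelated to the device, the bias may be zero or reversed, as the table shows.
- **Other data exist.** The device logs dispensing (section 3.3.1), dispensed over prescribed doses is a listed outcome, and section 4 mentions interviews and promises cautious interpretation. Logs can reveal non-use, but not what the user thought of the device. The interviews have no stated timing or respondents, and caution does not replace missing answers.
- **Scope.** Section 2.3 does not say that the questionnaire is about the device or is confined to SME+K; its place under usability suggests the former. Consent and some appendix pages were not available to this review, so a withdrawal procedure there cannot be excluded.
- **Blinding.** Section 3.1 wants the researcher unaware of allocation where possible, and asking about the device on a call could reveal it. This is a real cost, although a visit to a home where the device may be in view already strains that aim.

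None of this supplies a post-use answer for a participant missed at 3 months.

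**Conclusion.** The point holds as a cheap improvement. The plan schedules one post-use reading of a primary-objective measure, and its rule for non-completers gives either no value or a pre-use one. The result is a risk of overstated acceptability, conditional on early leavers being less satisfied.

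The size, up to about 19 of 94 SME+K participants and roughly 4 to 12 points, rests on three assumptions: that compliance at West Park means 3-month completion, that the questionnaire concerns the device, and that the completer-leaver gap is 20 to 60 points. With no gap the bias is zero. The documents do not establish how many people will stop using the device, or that those who do will be lost.

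**What to change.** 1. **Collection (section 3.4).** When a participant stops using the device or withdraws, give the satisfaction and acceptance questionnaire by phone around the next bi-weekly call, and record the reason. Still make the 3-month visit to those who stop the device but remain in the study.
2. **Missing data (section 4).** Exclude this questionnaire from LOCF, so that no pre-discharge answer counts as an outcome.
3. **Reporting.** Report device discontinuation among all participants randomised to SME+K. Give acceptability on observed post-use answers, with a sensitivity analysis that counts stoppers without an answer as not accepting. That rule suits a sensitivity analysis better than the main result, since it builds in the opposite bias for people who left for unrelated reasons.

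**Cost.** Some wording changes and one short questionnaire on a contact that already exists, for perhaps 19 SME+K participants at West Park on the reading above. The downsides are mixed phone and in-person administration, a possibly lower acceptability figure, and possible unblinding of the research assistant. The last can be limited by having a team member who already knows the allocation ask the device questions, or by asking them after the adherence questions.

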3.1 Recruitment

Potential West Park study participants will initially be identified by clinical staff referring to SME. Apparently appropriate subjects will be informed of the study by a member of their care team and, if interested, identified as wishing to receive additional information about the study during their initial meeting with the SME OT. The OT will briefly explain the nature of the study and request consent for the study research assistant (RA) to contact the patient to provide additional details of the study objective and procedures. The RA will arrange to meet with patient expressing an interest in participating in the study to obtain written consent (see Appendix A) and conduct baseline measures. The OT and pharmacist delivering the SMP will be blinded to group assignment.

Potential CapitalCare study participants will be identified by the research team Occupational Therapist. The Occupational Therapist (OT) will share this information with the CapitalCare research assistant (RA) who will be in regular contact. The RA will acquire consent and collect baseline data from the client (see inclusion criteria and measures for definitions).

The study RA, who will be blind to the assignment of the client to either intervention or control group, will approach the potential participant to explain the study, its purpose and aims to obtain informed consent for the study. As far as possible to maintain, the researcher will be unaware of the designation of the client to the Karie or control group.

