2 METHODS

2.1 Design

This study will utilize a multi-site randomized controlled trial design. One week prior to discharge from inpatient rehab, consenting patients will be randomly assigned to receive medication self-management education only (SME) or medication self-management education + KARIE (SME+K).

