3.2 Subject Training

3.2.1 Self-Medication Education Program

West Park has a “Self-Medication Education Program” policy in place which seeks to establish independent medication SM capacity during the inpatient stay. Eligibility criteria for SME include a need to manage medications independently at home; stabilized on medication, as per

pharmacist/physician discretion; and mild-moderate cognitive/physical impairments, as per OT assessment. To determine SME eligibility, an OT and pharmacist completes the Interprofessional Screening for Self Medication Readiness (Appendix B) to determine self-management capacity. Eligible patients then receive training by an OT, followed by a 5-day self-medication performance assessment (Appendix C) by an RN prior to discharge. Following discharge, these patients are often referred to receive 24 OT outpatient therapy sessions for 3-months, on average.

CapitalCare will adopt the West Park “Self-Medication Education Program” program and documentation for purposes of this study. To determine SME eligibility, an OT, Pharmacist, or RN will complete applicable portions of the Interprofessional Screening for Self Medication Readiness (Appendix B) to determine self-management capacity. Eligible clients then will receive training by an OT, followed by a 5-day self-medication performance assessment (Appendix C) by an RN.

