3.2.2 Orientation to KARIE

Patients randomly assigned to receive SME+K will undergo Screening for Self Medication Readiness (Appendix A) to determine self-management capacity, will receive SME by an OT, followed by a 5-day self-medication performance assessment (Appendix B) by an RN prior to discharge, as described above (see “Self-Medication Program”). In addition, this group will receive orientation to the KARIE Automated Medication Delivery Device. Karie orientation will be integrated into SME and delivered by the study OT, [name].

For purposes of this evaluation of the AceAge medication dispensing device, the SME and recruitment strategy will provide for: 1) standardized eligibility assessment, training, and performance evaluation of SM capacity for experimental and control subjects, 2) introduction to the AceAge device in the inpatient setting for experimental subjects, and 3) standardized medication adherence assessment during the 3-month outpatient follow-up period.

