Evaluation:	Yes	No	Initials	Date	Comments
Eligible for SMP (all 'yes' except for shaded boxes; *at the discretion of the team)					If not, name interventions:

SELF-MEDICATION PATIENT PERFORMANCE RECORD

LEVEL 1 (Minimum 48 hours) LEVEL 2 (Minimum 72 hours) Dosette Vial/Bottle Blister pack

START A NEW PAGE WHEN:

progressing a patient to a new level* AND/OR *when changing medication containers (dosette vs. blister back vs. bottle)

Date yy/mm/dd	Time	Initials/Designation	Time	Initials/Designation	Time	Initials/Designation	Time	Initials/Designation
Day no.  ____	 Independent  Physical assistance  Verbal cueing re: compartment  (Level 2): Cueing to initiate  Other: _____		 Independent  Physical assistance  Verbal cueing re: compartment  (Level 2): Cueing to initiate  Other: _____		 Independent  Physical assistance  Verbal cueing re: compartment  (Level 2): Cueing to initiate  Other: _____		 Independent  Physical assistance  Verbal cueing re: compartment  (Level 2): Cueing to initiate  Other: _____	

Date yy/mm/dd	Time	Initials/Designation	Time	Initials/Designation	Time	Initials/Designation	Time	Initials/Designation

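### At West Park, the stated blinding of the OT who delivers the self-medication education is not supported, because KARIE orientation is built into that education

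*Combined protocol and SAP*

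**What the plan says.** Section 2.1 compares education alone (SME) with education plus the device (SME+K), so the education is common to both arms. On timing it says: "One week prior to discharge from inpatient rehab, consenting patients will be randomly assigned".

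Section 3.1, in the paragraph on West Park recruitment, says: "The OT and pharmacist delivering the SMP will be blinded to group assignment". The sentence carries no qualification. The abbreviation SMP is not spelled out there, but section 3.2.2 refers back to the self-medication programme by name and the appended eligibility form uses the same abbreviation, so it means the education.

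Section 3.2.1 gives the training to an OT: "Eligible patients then receive training by an OT, followed by a 5-day self-medication performance assessment (Appendix C) by an RN prior to discharge". Section 3.2.2 repeats this for patients assigned to SME+K, who "will receive SME by an OT, followed by a 5-day self-medication performance assessment (Appendix B) by an RN prior to discharge". (The appendix letters differ between the two sections; that does not affect this point.) It continues: "In addition, this group will receive orientation to the KARIE Automated Medication Delivery Device". On how that is done: "Karie orientation will be integrated into SME and delivered by the study OT".

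The same section also promises standardised training for experimental and control subjects, without giving a method.

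**The concern.** An educator cannot include device training in one arm's education, leave it out of the other's, and remain unaware of the arm. Section 3.1 therefore claims a safeguard that section 3.2.2 appears to remove.

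Two things are at stake. First, because the education is common to both arms, a trainer who knows the allocation could give it with different content, time or emphasis. Any difference between arms would then mix the effect of KARIE and its orientation with the effect of uneven education. Self-efficacy for medication use and satisfaction are listed under the primary objective, and several self-report scales under the adherence objective; all are open to what the educator says and how long it takes. Second, a report that repeats section 3.1 would claim a blinding that the procedures do not deliver. Section 3.1 hedges the researcher's blinding but not the OT's, so a reader would take the OT claim as firm.

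**Working it through.** The point is textual. The plan gives no alpha, power, effect size or standard deviation, and no figure depends on the blinding claim, so there is no plan figure to reproduce. The check is to set the sections side by side.

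1. **Who is said to be blinded?** The OT and the pharmacist who deliver the education at West Park (3.1).
2. **Who delivers the education?** An OT, in general (3.2.1) and in the SME+K arm (3.2.2).
3. **Who receives KARIE orientation?** SME+K only (3.2.2).
4. **How is it delivered?** Inside the education, by the study OT (3.2.2).
5. **What follows?** From 2 to 4, an OT giving the education with orientation built in knows that the patient is in SME+K. The same OT giving it without orientation can infer SME only. The claim in 1 therefore fails for that OT in both arms. Nothing in 2 to 4 concerns the pharmacist.
6. **Does timing protect the claim?** It would if the education were finished before allocation was known. Section 2.1 places randomisation 7 days before discharge. The performance record sets minimum periods of 48 h and 72 h for its two levels: 48 + 72 = 120 h, and 120 / 24 = 5 days, which agrees with the 5-day assessment in 3.2.1. If OT training starts only after randomisation, 7 − 5 = 2 days remain for it. Section 3.2.2 describes patients already assigned to SME+K who then undergo screening, education and assessment. On the other side, section 3.1 has a first meeting with the SME OT before consent, so some contact comes before allocation. No section says when training starts or ends relative to allocation. Whatever the start, the arm-specific orientation has to follow allocation, and if it is part of the education, so does that part of the education.
7. **Is another safeguard described?** The visible text has no separate orientation session, no handover between two OTs, no scripted education and no check of its delivery by arm. It has the promise of standardised training (3.2.2) and an existing West Park programme with set forms (3.2.1).

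**The case against.** The strongest reply is that there may be two OTs. Section 3.1 speaks of the SME OT; section 3.2.2 speaks of an OT for the education and of the study OT for KARIE. The documents never say that these are one person, and integration into a programme need not mean a joint session. If the study OT alone handled the device, the SME OT could stay blinded. This is possible, but the plan does not describe it: building orientation into the education works against it, and no separation is laid down. If it is what the sponsor intends, the protocol has to say so. What stands is that the blinding is unsupported as written; it has not been shown to be impossible.

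A second reply is that trainers who teach a visible device usually cannot be blinded, that outcomes are collected by an RA whose blinding is stated separately, and that training is to be standardised from an established programme. This lowers the concern about biased delivery. It does not make the sentence in 3.1 correct, and it is itself an argument for deleting the sentence.

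Three stronger readings are tempting:

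- **That the blinding fails at both sites and for all the staff named.** The sentence stands in the West Park paragraph, the CapitalCare paragraph claims no OT blinding, and nothing visible contradicts the pharmacist's blinding.
- **That randomisation precedes all of the education.** Section 3.2.2 leans that way, but the plan does not fix the order.
- **That the bias can be sized against a detectable difference.** The documents give neither an effect of uneven education nor a standard deviation or power target, so any percentage would rest on an assumed effect.

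**Conclusion.** The concern holds for the OT at West Park. Section 3.1 claims a blinding that section 3.2.2, as written, does not support. This rests on reading SMP as the self-medication education and on taking the integration of orientation at its word; both follow from the text.

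Uneven delivery of the education is a risk for self-efficacy, satisfaction and self-reported adherence. It has not been shown to occur, and its size cannot be derived from the documents. A reader might infer that the comparison of arms is therefore biased; the documents do not support that. The education at CapitalCare may carry a similar risk wherever orientation is built into it, but there is no blinding claim there to correct. The planned sample size is not affected. The correction should be made because it is cheap and because the blinding statement would otherwise pass into the trial report.

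**What to change.** Reconcile sections 3.1 and 3.2.2 in one of two ways.

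**(a) Correct the claim.** Delete the OT from the blinding sentence in 3.1 and report the OT as unblinded. This is a change of wording only.

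**(b) Make the claim true.** Amend 3.2.2 so that the SME OT gives the same device-free education to both arms without knowing the allocation, and the study OT gives KARIE orientation to SME+K only, in a separate session that is not part of the education. The performance record lists only "Dosette Vial/Bottle Blister pack" as containers, which is compatible with device-free education, although as an existing programme form it is weak support. The cost is some scheduling before discharge and the requirement that the study OT is not the SME OT. If that is not feasible, use (a).

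Under either option, state for each site which staff are blinded. A short log of the content and time of the education by arm would let the report show whether delivery was alike; this is useful but is not needed to remove the contradiction.

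Completing the education and the 5-day assessment before allocation is opened would protect the education further, but it is optional. It would require the one-week randomisation timing in 2.1 to be amended. If allocation moved later, orientation would compete with the data collection session 24 to 48 hours before discharge (3.4) and with the pharmacist's preparation of the KARIE cartridge (3.3.1).
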